#### CONFIDENTIAL

This document is confidential. Do not disclose or use except as authorized.

- Calculated creatinine clearance  $\geq$  30 mL/min
- 3.1.5 Ability to understand and the willingness to sign a written informed consent before performance of any study-related procedure not part of normal medical care, with the understanding that consent may be withdrawn by the subject at any time without prejudice to future medical care.
- 3.1.6 Female patients who are postmenopausal for at least 1 year before the screening visit or are surgically sterile. Females of childbearing potential\* must have a negative serum or urine pregnancy test with a sensitivity of at least 50 mIU/mL within 10 14 days and again within 24 hours prior to prescribing lenalidomide for Cycle 1 (prescriptions must be filled within 7 days as required by Revlimid REMS®) and must either commit to continued abstinence from heterosexual intercourse or begin TWO acceptable methods of birth control, one highly effective method and one additional effective method AT THE SAME TIME, at least 28 days before she starts taking lenalidomide. Female patients must agree to practice two effective methods of birth control from the time of signing the informed consent form though 90 days after the last dose of study drug
  - \* *A female of childbearing potential is a sexually mature female who:* 
    - Has not undergone a hysterectomy (the surgical removal of the uterus) or bilateral oophorectomy (the surgical removal of both ovaries) or
    - Has not been naturally postmenopausal (amenorrhea following cancer therapy does not rule out childbearing potential) for at least 24 consecutive months (i.e., has had menses at any time during the preceding 24 consecutive months)
- 3.1.7 All study participants must be registered into the mandatory Revlimid REMS® program, and be willing and able to comply with the requirements of the REMS® program.
- 3.1.8 Females of reproductive potential must adhere to the scheduled pregnancy testing as required in the Revlimid REMS® program.

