# The participant will be requested to maintain a medication diary. The medication diary and empty pill containers will be returned to clinic staff at the end of each cycle.

Stem cell collection using standard mobilization procedures of the Institute can be performed for patients who are eligible and will be performed at the time of best remission or after 9 cycles of therapy. Patients may delay treatment for up to 3 weeks after stem cell collection is complete.

During maintenance, patients may return to clinic every 3 cycles beginning with cycle 10. If this option is utilized, a 3-month supply of ixazomib will be supplied by the investigational pharmacy at each visit. Lenalidomide may be shipped from the investigational pharmacy to the patient's home for each cycle the patient does not return to clinic, according to local practice.

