#### 5.2.2 Lenalidomide

Lenalidomide will be given as a single daily oral dose of 25 mg per day on days 1–21 followed by a 7-day rest period for cycles 1–9 and 15 mg per day on days 1-21 for cycles 10–24. A window of +/-7 days is allowed, except cycles 1 and 2 which will be +/-3 days. Dose modification guidelines are described in Section 6.2 (Dose Modifications/Delays).

Lenalidomide capsules should be swallowed whole, and should not be broken, chewed or opened. Administration of lenalidomide will be at approximately the same time each day. Drug may be taken with or without food. If a dose is missed and less than 12 hours has elapsed since the missed dose, the patient can take the dose for that day. If more than 12 hours has elapsed since missing a dose at the normal time, the patient should not take the dose, but take the next dose at the normal time on the following day. If a dose is missed, it should be taken as soon as possible on the same day. If a dose is vomited, the dose should not be made up and the participant should continue with the regular schedule of the drug at the next dose. A drug diary will be provided to participants to record oral administration of doses.

Participants who take more than the prescribed dose of lenalidomide should be instructed to seek emergency medical care if needed and contact study staff immediately. Participants experiencing adverse events may need study treatment modifications (see Section 6.2).

Lenalidomide related resources will be provided to all patients prior to receiving lenalidomide therapy as part of the Revlimid REMS program. For more information regarding program registration and drug ordering, refer to section 8.2.

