#### 8.2.8 Ordering

Lenalidomide (Revlimid®) will be provided to research subjects for the duration of their participation in this trial at no charge to them or their insurance providers. Lenalidomide will be provided in accordance with the Celgene Corporation's Revlimid REMS® program. Per standard Revlimid REMS® program requirements, all physicians who prescribe lenalidomide for research subjects enrolled into this trial, and all research subjects enrolled into this trial, must be registered in, and must comply with, all requirements of the Revlimid REMS® program.

Drug will be shipped on a per patient basis by the contract pharmacy to the clinic site.

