#### Only enough lenalidomide for one cycle of therapy will be supplied to the patient each cycle.

Lenalidomide will be shipped directly to the clinic site. Bottles will contain a sufficient number of capsules for one cycle of dosing.

During maintenance, patients may return to clinic every 3 cycles beginning with cycle 10. If this option is utilized, lenalidomide may be shipped from the investigational pharmacy to the patient's home for each cycle the patient does not return to clinic, according to local practice.

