#### **10. STUDY CALENDAR**

Screening evaluations are to be conducted within 28 days prior to registration. If bone marrow biopsy, research aspirate, and imaging assessments are completed within 6 weeks of registration, they do not need to be repeated at screening. Baseline assessments are to be conducted on C1D1 of initial therapy. C1D1 must occur within 6 weeks of registration. If screening assessments are performed within 7 days of C1D1, disease assessments do not need to be repeated. All assessments must be performed prior to administration of any study medication. Study assessments and medications should be administered within +/- 3 days (during cycles 1-2) and +/- 7 days (during cycles 3-24) of the protocol-specified date, unless otherwise noted. See below for detailed scheduled of assessments. Study medications will be administered according to the schedule and guidelines outlined in Section 5.

|   | Pre-registration                             |  | Cycles 1-24 (28 days)       |   |   |                             | Event
Monitoring                            |
|---|--|--|---|---|---|-----------------------------|--|
| Tests and procedures  | ≤ 28
days
prior to
registrat
ion | ≤ 21
days
prior to
registrat
ion | Day 1 of
cycles 1-
9  | Every 3
months for
Cycles 10-
24 | Cycle 10
Day 1/ Or
to
confirm
CR  | End of
Tx (± 2
weeks) | Every 3
Months (±
2 weeks)  |
| History and exam, height, weight.
Performance Status   | Х  |  | Х                                       | Х   |   | Х                           | X  |
| Toxicity Notation   |  |  | Х                                       | Х   |   | Х                           |  |
| Hematology group (WBC w/ diff, PLT, Hgb, ANC)   |  | Х  | Х                                       | Х   |   | Х                           | Х  |
| Chemistry   |  | Х  | Х                                       | Х   |   | Х                           | Х  |
| Direct & total bilirubin    |  | Х  | Х                                       | Х   |   | Х                           |  |
| Free light chain assay  |  | Х  | Х                                       | Х   |   | Х                           | Х  |

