| Serum and Urine Immunofixation
(SPEP and UPEP) with quantitative
immunoglobulins  |  | Х  | Х                                       | Х   |   | Х                           | X  |
| β2M and LDH   |  | Х  | Х                                       | Х   |   | Х                           |  |
| Metastatic Bone Survey and MRI of
the Full Spine
OR
PET/CT      | Х  |  |   |   |   | Х                           |  |
| EKG   |  | Х  |   |   |   | Х                           |  |
| Serum or urine pregnancy test    |  | Х  | Х                                       |   |   |                             |  |
| Unilateral bone marrow aspirate and biopsy    | Х  |  |   |   | Х   | Х                           |  |
| Research bone marrow aspirate   | X                                |  |   |   | X   | X               |  |
| Research Blood    | X                                |  | X                           | X                             | X   | X               |  |
| Buccal Swab    | Х  |  |   |   |   |                             |  |

1- Cycle 1, Day 1 laboratory values need to meet eligibility criteria

2- Direct bilirubin to be obtained if total bilirubin is abnormal

3- Scheduling allows for +/- 3 days cycles 1-2 and +/- 7 days for cycle 3 and beyond

4- Chemistry includes sodium, potassium, chloride, bicarbonate, bun, creatinine, calcium, glucose, albumin, ALT (SGPT), total protein, AST (SGOT), total bilirubin, magnesium, and phosphorus

5- These procedures should also be done at any time during the course of the study to confirm CR Aspirate should be collected and sent out to Adaptive for MRD analysis at baseline and at time of VGPR or suspected CR

6- Research bone marrow aspirate and biopsy at the same time of clinically indicated bone marrow biopsy and to confirm response

7- Peripheral blood samples for correlative studies

8- If BM biopsy performed within 3 weeks of C10D1, or confirmation of CR BM biopsy performed within 3 weeks of stem cell collection, do not need to repeat BM biopsy

9- If the participant's disease response is not followed primarily via a UPEP and Urine immunofixation, these tests may be done only at screening, end of treatment, and as clinically indicated during treatment and follow-up

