10-The buccal swab can be performed at any timepoint during study participation

11-Pregnancy tests are only required for women of childbearing potential 10-14 days prior to registration, 24 hours prior to prescribing lenalidomide for C1 and every day 1 post C1

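### The calendar leaves the pregnancy-test row blank for cycles 10-24 although footnote 11 requires a test every cycle, and two different menopause thresholds are in force

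*Combined protocol and SAP*

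**What the plan says.** **Calendar.** The row "Serum or urine pregnancy test" carries a mark in the 21-day pre-registration column and in the column for Day 1 of cycles 1-9. Its cells for the quarterly visits of cycles 10-24 and for the cycle 10 marrow assessment are empty. Footnote 11 limits the tests to women of childbearing potential and times them "10-14 days prior to registration, 24 hours prior to prescribing lenalidomide for C1 and every day 1 post C1".

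**Exposure and supply.** Section 5.2.2 gives lenalidomide at "15 mg per day on days 1-21 for cycles 10–24". Section 5.1 states: "During maintenance, patients may return to clinic every 3 cycles beginning with cycle 10". Sections 5.1 and 8.2.8 allow lenalidomide to be sent to the patient's home for a cycle without a visit. Section 8.2.8 also limits supply: "Only enough lenalidomide for one cycle of therapy will be supplied to the patient each cycle".

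**Other testing duties.** Section 3.1.8 states: "Females of reproductive potential must adhere to the scheduled pregnancy testing as required in the Revlimid REMS". Section 8.2.8 says that prescribers and subjects "must be registered in, and must comply with, all requirements of the Revlimid REMS". The testing schedule under that program is not reproduced in the protocol.

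**Menopause.** The first sentence of 3.1.6 refers to women at least 1 year postmenopausal, and the pregnancy item in 5.4 lists that status as sufficient by itself. The starred definition in 3.1.6 counts a woman as of childbearing potential until she has been naturally postmenopausal for 24 consecutive months. Women who meet that definition must abstain or use two methods of birth control, and must be tested.

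**The concern.** Sites commonly schedule visits and procedures from the calendar grid. For maintenance, this grid shows no pregnancy test, while the note attached to the same row asks for one every cycle. The mismatch falls in the phase with the least site contact. Under 6.1, the cycle-start criteria need be met only at the quarterly visits in maintenance, local guidelines apply in between, and lenalidomide has no protocol-specific criteria for starting a cycle. A coordinator who works from the grid could therefore miss, or fail to record, a test that the protocol requires.

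The menopause thresholds bear on the same point, because footnote 11 applies only to women of childbearing potential. A woman 12 to 24 months without menses meets the 5.4 list with no contraception, yet falls inside the 3.1.6 definition, which asks for contraception and testing.

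The stake is fetal exposure to a drug whose teratogenic potential the protocol itself names in 3.2.6. Efficacy inference is not at stake.

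**Working it through.** The plan states no figure of its own to reproduce. The check is a cycle count and a comparison of texts.

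**Is the blank real?** Neighbouring rows, such as chemistry and β2M with LDH, keep their marks in the quarterly column for cycles 10-24. The empty cell is therefore unlikely to be a loss in reading the table.

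**Inputs**
- Cycles: 9 induction + 15 maintenance = 24 (1.4).
- Tests required after cycle 1: Day 1 of each later cycle (footnote 11).
- Tests marked after cycle 1: Day 1 of cycles 2-9 (calendar row).
- Minimum maintenance visits: every third cycle from cycle 10 (5.1). Appendix B uses the same spacing for research blood.

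**Counts for a woman who completes all 24 cycles**

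| Quantity | Calculation | Result |
|---|---|---|
| Required after C1 | cycles 2-24: 24 - 1 | 23 |
| Marked after C1 | cycles 2-9: 9 - 1 | 8 |
| Unmarked | 23 - 8 | 15 |
| Share unmarked | 15/23 | 65% |
| Visits if the quarterly option is used | cycles 10, 13, 16, 19, 22 | 5 |
| Unmarked tests in no-visit cycles, maximum | 15 - 5 | 10 |
| Share of all required, maximum | 10/23 | 43% |

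The 10 no-visit cycles would be 11, 12, 14, 15, 17, 18, 20, 21, 23 and 24. Quarterly attendance is optional, so the range is 0 to 10.

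**Would a mark in the existing column be enough?** The only recurring maintenance column is quarterly. A mark there would show 8 + 5 = 13 of the 23 tests (13/23 = 57%). The row would still disagree with its footnote, so a written annotation is needed.

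**Menopause rules side by side**

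| Months since last menses | Opening of 3.1.6, and 5.4 (1 year) | Definition in 3.1.6 (24 months) |
|---|---|---|
| Under 12 | not postmenopausal | of childbearing potential |
| 12 to under 24 | postmenopausal; 5.4 asks for no contraception | of childbearing potential: abstinence or two methods, and tests |
| 24 or more | postmenopausal | not of childbearing potential |

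The two rules differ over a window of 24 - 12 = 12 months. A site that applies 24 months satisfies both.

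**The case against.** The strongest reply is that the requirement is already there. Footnote 11 is attached to this row, names the population and has no end at cycle 9. Section 3.1.8 makes the REMS testing schedule mandatory, 8.2.8 binds prescribers and subjects to the whole program, and lenalidomide is supplied one cycle at a time. On this view, the percentages count empty cells and not missed tests, and harm would require a site to overlook the footnote, 3.1.8 and REMS together. This stands, and it limits the claim. It does not remove the mismatch between a safety row and its own footnote.

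On menopause, the pregnancy item in 5.4 opens with the unknown effects of ixazomib and speaks of study drug, a term that 5.2.1 applies to ixazomib capsules. The 24-month definition is attached to the sentence in 3.1.6 about prescribing lenalidomide. The text can therefore be read as two drug-specific rules that apply together, and the 1-year opening of 3.1.6 is a fragment that instructs nothing. That reading is fair, and it means that a direct contradiction should not be asserted. But every participant is assigned both drugs, and the protocol never says that the rules are drug-specific or which one prevails.

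A reader might also infer that lenalidomide can be shipped home with no test having been done. The documents do not support that: the testing duty covers those cycles, and the REMS schedule, which might itself control dispensing, is not available to check.

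**Conclusion.** Both inconsistencies hold and should be corrected. The calendar row omits 15 of the 23 tests after cycle 1 that its footnote requires (65%), and between 0 and 10 of the 15 can fall in cycles without a visit. These counts assume a woman of childbearing potential who completes 24 cycles; the upper figure also assumes that she attends only quarterly from cycle 10. The menopause thresholds leave a 12-month window in which the governing rule is not stated.

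A reader who sees only the grid might conclude that pregnancy testing stops after induction. It does not: footnote 11, 3.1.8 and 8.2.8 all require it. The defect is in how the schedule is displayed and in one threshold. The documents do not give the number of women concerned, and it is probably small. Type I error, power, sample size and the primary analysis are unaffected.

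**What to change.** 1. Annotate the pregnancy-test row for cycles 10-24: *every cycle for women of childbearing potential, including cycles without a clinic visit (local test), per footnote 11 and REMS*.
2. Use 24 months in the opening of 3.1.6 and in 5.4, to match the definition of childbearing potential.

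Test timing should stay with footnote 11 and REMS. A new rule that ties a test to a fixed number of days before home shipment is not recommended. It would be written without sight of the REMS schedule, could create a second testing interval beside it, and would loosen the Day 1 timing that the footnote already sets.

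The cost is a calendar and wording amendment. For women already treated as of childbearing potential, the number of tests stays at the footnote's 23 after cycle 1. Sites must record local results in up to 10 no-visit cycles per woman concerned. Where a site had applied the 1-year rule, a few more women would have to meet the contraception requirement and be tested.

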#### CONFIDENTIAL

This document is confidential. Do not disclose or use except as authorized.
12-A CD of scans at screening and end of treatment is required to be sent to the lead site for central review Screening scans should be sent with the eligibility packet to the lead site-This requirement includes a full body skeletal survey in addition to spinal MRI OR the patient may have only a low dose PET CT

Note: Research blood and bone marrow studies of all cycles after cycle 1 are voluntary and do not exclude patients from participating

13 – Participants unable to come in for follow up every 3 months can be allowed to come in every 6 months for follow up at PI discretion in accordance with standard of care follow-up frequency

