#### **1.4 Duration of Study**

A treatment cycle is defined as 28 consecutive days.

Patients will receive 9 cycles of induction therapy followed by 15 cycles of maintenance therapy for a total of 24 months.

For treatment cycles 1 and 2, a +/-3 day window is allowed. For treatment cycles 3 through 24, a +/-7 day window is allowed. Treatment plan is designed to be administered on an outpatient basis, however if necessary, may be given as inpatient.

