### **11. MEASUREMENT OF EFFECT**

### 11.1 Development of symptomatic disease

In this study, the final endpoint is development of symptomatic MM that requires therapy. This is defined as one of the following criteria (CRAB and Myeloma defining events< MDE):

- Increased calcium levels (corrected serum calcium >0.25 mmol/dL above the upper limit of normal or >.275 mmol/dL) due to myeloma
- Renal insufficiency (attributable to myeloma);
- Anemia (Hb 2g/dL below the lower limit of normal or <10g/dL) due to myeloma
- Bone lesions (lytic lesions or generalized osteoporosis with compression fractures)
- Or any MYELOMA DEFINING EVENTS (MDE) as follows:
  - $\circ$  Clonal bone marrow plasma cell percentage > 60%
  - An abnormal FLC-ratio  $\geq 100$  (involved kappa) or < 0.01 (involved lambda)
  - 2 or more focal lesions on MRI or PET-CT studies

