### 11.2.2 Methods for Evaluation of Measurable Disease

All baseline evaluations should be performed on Cycle 1, Day 1 of initial therapy. Response will be assessed by M-protein quantification, protein electrophoresis and immunofixation from serum and a 24-hour urine collection. A serum sample for FreeLiteTM testing will be obtained. In addition, bone marrow aspiration and biopsy, as well as skeletal survey will be performed to determine overall response or confirm response.

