### 11.2.3.1 International Myeloma Working Group Response Criteria

Response criteria for all categories and subcategories of response except CR are applicable only to patients who have 'measurable' disease, as defined in Section 11.1.1 All response categories require two consecutive assessments made at any time before the institution of any new therapy; all categories also require no known evidence of progressive or new bone lesions if radiographic studies were performed. Radiographic studies are not required to satisfy these response requirements.

| Response              | Criteria for Response  |
|-----------------------|--|
|                       | CR as defined below plus normal free light chain ratio and absence of      |
|                       | clonal cells in bone marrow * by immunohistochemistry or                   |
|                       | immunofluorescence.**  |
| Stringent CR
(sCR) | *Confirmation with repeat bone marrow biopsy is not needed.                |
|                       | **Presence/absence of clonal cells is based upon the $k/\lambda$ ratio. An |
|                       | abnormal k/l ratio by immunohistochemistry and/or immunofluorescence       |
|                       | requires a minimum of 100 plasma cells for analysis. An abnormal ratio     |
|                       | reflecting presence of an abnormal clone is $k/\lambda$ of > 4:1 or < 1:2. |
|                       | Negative immunofixation on the serum and urine and disappearance of        |
| Complete              | any soft tissue plasmacytomas and $\leq 5\%$ plasma cells in bone marrow.  |
| Response (CR)         |  |
|                       | *Confirmation with repeat bone marrow biopsy is not needed.                |
|                       | Serum and urine M-protein detectable by immunofixation but not on          |
| Very Good Partial     | electrophoresis or 90% or greater reduction in serum M-protein plus        |
| Response (VGPR)       | urine M-protein level <100mg per 24 hours.                                 |

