### 13.1.1 Analysis of Primary Endpoint

Time to progression (TTP) is defined as the time from protocol therapy initiation until documented progression, censored at date last known progression-free for those who have not progressed. At time of final analysis, the 2-year progression-free rate will be estimated using the Kaplan-Meier method with 95% confidence interval. All patients who have received one dose of study treatment will be included for the TTP analysis, including those who die or are lost to follow-up within 2 years.

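### The last scheduled imaging and bone marrow are tied to the end of cycle 24, not to the 2-year landmark, so long permitted delays can push them past day 730

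*Combined protocol and SAP*

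**What the plan says.** **Endpoint.** Section 13.1.1 states that "Time to progression (TTP) is defined as the time from protocol therapy initiation until documented progression", and that "the 2-year progression-free rate will be estimated using the Kaplan-Meier method with 95% confidence interval". The event is dated when it is documented. Under section 11.1, lytic lesions, "2 or more focal lesions on MRI or PET-CT studies" and clonal marrow plasma cells above 60% all count as progression.

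**Assessments.** In section 10, the row beginning "Metastatic Bone Survey and MRI of" (with PET/CT as the alternative) is marked before registration and at End of Tx only. It is blank for cycles 1–9, cycles 10–24, the cycle 10 day 1/CR column and event monitoring. Footnote 12 matches this: "A CD of scans at screening and end of treatment is required to be sent to the lead site for central review". The clinical marrow row is marked before registration, at cycle 10 day 1 or to confirm CR, and at End of Tx. Outside the calendar, section 11.2.2 says that marrow "as well as skeletal survey will be performed to determine overall response or confirm response", with no date given. Section 11.2.3.1 adds: "Radiographic studies are not required to satisfy these response requirements".

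**Treatment length and delays.** Section 1.4: "Patients will receive 9 cycles of induction therapy followed by 15 cycles of maintenance therapy for a total of 24 months". Section 5.5 ends treatment by cycle count (24) or on an off-therapy criterion. Delays are allowed for mobilization (up to 6 to 8 weeks, section 5.3), after stem cell collection (up to 3 weeks, section 5.1), for toxicity (3 weeks, longer after discussion with the Principal Investigator, section 6.1) and for non-AE reasons (up to 14 days, section 6.1). No total is set.

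**The concern.** The primary endpoint is fixed on the calendar, while the last scheduled look for silent bone disease and marrow progression is fixed to a cycle count that can slip. If the look slips past 2 years, progression already present by day 730 but not yet documented is dated after the landmark, and the patient counts as a success. The trial has one arm, so no control group shares the shift. Progression found by the laboratory tests at the 3-monthly visits, or through symptoms, is not affected.

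**Working it through.** **The plan's own figure.** Section 13.1 gives 53 eligible patients and power 0.91 for 50% versus 70% at a type I error of 5%. The exact one-sided binomial reproduces this with success at 33 or more of 53: P(X ≥ 33 | 0.50) = 0.0492 and P(X ≥ 33 | 0.70) = 0.914. Then 53/0.95 = 55.8, or 56 patients. The timing issue changes none of these numbers.

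**Inputs for timing.** Cycle length 28 days and 24 cycles (sections 1.4 and 5.5); End of Tx window ± 14 days (section 10); landmark 2 years = 730 days from first dose (section 13.1.1).

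**Formula.** Nominal day = 24 × 28 + total delay = 672 + delay. Window = nominal day ± 14.

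| Total delay | Example | Nominal day | Window |
|---|---|---|---|
| 0 | on schedule | 672 | 658–686 |
| 42 days | 6-week mobilization, or two 3-week toxicity holds | 714 | 700–728 |
| 56 days | 8-week mobilization | 728 | 714–742 |
| 63 days | three 3-week toxicity holds | 735 | 721–749 |
| 70 days | 8-week mobilization plus 14 days non-AE | 742 | 728–756 |
| 77 days | 8-week mobilization plus one 3-week toxicity hold | 749 | 735–763 |

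The toxicity rows read the 3-week limit as applying to each hold.

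**Thresholds.**
- Late edge passes day 730: delay > 730 − 672 − 14 = 44 days (6.3 weeks).
- Nominal day passes day 730: delay > 730 − 672 = 58 days (8.3 weeks).
- Whole window passes day 730: delay > 730 − 672 + 14 = 72 days (10.3 weeks).

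The 77-day row does not require adding the 3 weeks in section 5.1 to the 6 to 8 weeks in section 5.3. It uses mobilization (56) plus one toxicity hold (21).

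**Effect per patient.** Section 13.1.1 analyses everyone who received a dose, so take n = 56. With no censoring before day 730, one misdated patient adds 1/56 = 1.8 percentage points to the 2-year rate, and two add 2/56 = 3.6.

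**The case against.** The strongest reply is that the plan as written puts the assessment before the landmark. On schedule the window closes on day 686, and even the full 8-week mobilization allowance alone gives a nominal day of 728. A toxicity delay beyond 3 weeks leads by default to stopping treatment, which brings End of Tx forward unless the Principal Investigator decides otherwise. This stands: late assessments are a tail case. An affected patient also needs progression present by day 730 that laboratory tests, symptoms, a response-driven skeletal survey or a clinically prompted scan did not reveal earlier.

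Three stronger readings are tempting, and the documents do not support them.

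- **A calendar cap of 24 months.** A reader might take the 24 months in sections 1.4 and 5.1 as calendar time, which would put End of Tx at about day 730 with no delay (window 716–744). But section 1.4 equates 24 months with 9 + 15 cycles, Table 8 runs maintenance over cycles 10–24, and section 5.5 counts 24 cycles.
- **Upward bias against the 50% null.** The 50% rests on a published median time to progression of 1.9 years (section 13.1). The documents do not say how that cohort was imaged. If its progressions were mainly found clinically, a scheduled scan could work in the opposite direction. The upward shift is shown only relative to an assessment made by day 730.
- **A known inflation of type I error.** If 0.1%, 1% or 2% of all patients were misdated, the 33-of-53 rule would give 0.051, 0.066 or 0.087 in place of 0.049. Those shares are pure assumptions (1% of 56 is 0.56 of a patient). The rule is also a reconstruction, whereas the planned analysis is a Kaplan-Meier estimate with a confidence interval.

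**Conclusion.** The point holds as a cheap improvement. Because total delay is uncapped and nothing ties imaging or marrow to 2 years, the last scheduled assessment of both can fall after day 730: possibly beyond 44 days of total delay, nominally beyond 58 and certainly beyond 72. Silent progression first documented then is counted as progression-free at 2 years. Each such patient adds about 1.8 percentage points, assuming 56 analysed and no earlier censoring. How many patients this would be cannot be derived from the documents; it is probably few. A delay that leaves the assessment on or before day 730 does no harm and brings it closer to the landmark. The conclusion rests on the 24-cycle reading and on dating events by documentation.

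**What to change.** Add one footnote to the imaging row and the clinical bone marrow row of section 10: *For patients still progression-free and on treatment, perform the End of Tx imaging and bone marrow no later than day 730 from first dose, even if cycle 24 is not finished.* It works whatever caused the delay. It adds no procedure, and the mobilization allowance stays as it is.

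**Cost.** Measured from the late edge of the window, the assessments move earlier by up to 742 − 730 = 12 days at an 8-week delay and up to 763 − 730 = 33 days at 11 weeks. At 8 weeks, cycle 24 is already complete on day 728. At 11 weeks it ends on day 749, with the last lenalidomide dose about a week before that, so the assessments would precede the last dose and would no longer show disease status after all treatment.

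**Not covered.** Patients who stop early have no imaging or marrow marked in event monitoring. Lesions arising between an on-schedule scan (about day 672) and day 730 are also still missed. Closing either gap would need an added procedure, which is not proposed here.

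As clarification only, cross-refer sections 5.1 and 5.3 and say whether the 3 weeks after collection lie inside the 6 to 8 weeks.
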